6.3.3 Safety Analysis

At least once every three months, we will review data storage and integrity. We will jointly review and report any unanticipated or adverse events (i.e. breach of privacy) to the CHOP IRB and NIMH in accordance with the NIMH reportable events policy. The frequencies of AEs will be summarized, although because this study is minimal risk, few are expected.

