5.1.3.1 *Computer Assisted Survey Instruments (baseline, 3-month and 6-month visit)*

The CASI will take approximately 40 minutes. These data will be entered directly into the secure REDCap platform by participants, with the option of having the survey read aloud and entered by study staff if the participant prefers. We will measure theorized intervention predictors and targets including demographics, sexual behavior, health activation, stigma, and self-efficacy. Surveys are:

Background/Demographics
Current Prevention Practices
Intentions Questions
Self-Efficacy
Knowledge and Attitudes Survey
Confidence in Safer Sex Scale
CRAFFT
General Self Efficacy Scale (GSES)
HIV Knowledge and Attitude
Modified ACES Inventory
Modified Partner Communication
Parent Adolescent Communication
Sexual Self Efficacy Scale
Youth Pediatric Symptom Checklist

Interpersonal Reactivity Index (IRI)
 Inventory of Parent and Peer Attachment (IPPA)
 Coaching Satisfaction Survey

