For Aim 3, all participants will be patients of CHOP primary care clinics, and thus can be rapidly referred to clinicians and social workers in case there is a need to intervene for an identified mental health issue. Our mood rating instrument, the PSC-17, does not include any assessment of suicidal ideation. However, if a participant discloses suicidal ideation, homicidal ideation, or abuse during an intervention session, the PI will be notified immediately, as well as the clinic social worker. Based on clinician assessment, participants who report suicidal ideation will be referred to the local Emergency Department or psychiatric crisis center, as needed. Any reports of child abuse will be reported to the clinic social worker and reported to ChildLine in accordance with Pennsylvania State Law. All participants will be provided mental health resources at the end of the first session, irrespective of their score on the PSC-17.

Participants will complete a modified version of the Adverse Childhood Experiences survey. To minimize the risk to participants that may arise regarding fear of disclosing a specific form of adversity, the study will utilize a modified version of the ACES questionnaire that has been validated in middle and high school students. The modified inventory is presented in 7 items. Within each item, participants are presented with a diagram including 2-4 circles. Each circle contains the description of an ACE, with language adapted from the cited inventories. The wording has been modified to be appropriate for the reading and comprehension abilities of 14 to 18-year-olds. Participants are instructed to read the ACE description contained in each circle, to think back on their entire life, and to decide if the

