The primary outcome for the RCT is the change in prevention self-efficacy between intervention and control conditions between the baseline and six-month (final) visits. We will compare the exposure variable of treatment group with the outcome variable of continuous score on the modified Generalized Self-Efficacy Scale at baseline, intermediate (e.g. three month), and six-month visits using mixed effects logistic regression models with a random intercept for patient and a random slope for time. In exploratory analyses, to determine if the mental health predictors impact the self-efficacy outcome, we will create separate mixed effects regression models to compare self-efficacy score for those with and without mood ratings consistent with depression on the PSC-17, high trauma (Adverse Childhood Experiences Scale score >4 vs not), and substance abuse (CRAFFT score >4) adjusting for treatment group and demographic characteristics including sex. In order to assess the impact of STI timing on the primary outcome of prevention self-efficacy, we will use linear regression models and days between STI diagnosis and the first coaching visit in the intervention group, adjusting for demographic covariates including sex and sexual orientation. Finally, we will assess if coaching may have a significant effect on other domains in the self-efficacy pathway of our model, by repeating the primary analysis above with scores for the Patient Activation Measure [PAM], and Confidence in Safer Sex Scale.

There will be no adjustment of p value for multiple comparisons given the exploratory nature of these analyses.

Secondary outcome analyses:

- Referral feasibility: Calculated as the number of potential participants referred to study staff over the number of patients with bacterial STI at the clinics during the study period. This denominator will be identified using the CHOP STI dataset.
- Recruitment feasibility: Calculated as the number of patients enrolled over the number of patients referred.

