9.4 Regulatory and Ethical Considerations

9.4.1 Data and Safety Monitoring Plan

This research project has no more than minimal risk to the participants. Throughout the study, risks (loss of confidentiality, psychologic distress etc.) to the participants will be monitored by the co-investigators with oversight and monitoring responsibility falling primarily on the PI of the research team. All study information will be stored on CHOP SAN drives, CHOP managed REDCap web application, password protected, and for paper copies and interview tapes in a locked cabinet in a locked office until information can be entered into electronic form.

Safety of research participants will be ensured through a Data and Safety Monitoring Plan consistent with NIMH guidelines. The PI will be responsible for ensuring that research adheres to this plan. We will train all research staff consenting participants to ensure all elements of informed consent are being performed. We will conduct routine monitoring of data throughout the study to ensure data is collected and recorded in adherence to the research plan, and that confidentiality of participants is maintained. Although the study is minimal risk, it still requires a high level of scrutiny and vigilance with respect to participant safety and data management, particularly given the sensitive nature of the data and enrollment of minor adolescents. At least once every three months, we will review data storage and integrity at the CHOP Roberts Center for Pediatric Research where the study team and the study data will reside. In addition, we will jointly review and report any unanticipated or adverse events (i.e. breach of privacy) to the CHOP IRB and NIMH in accordance with the NIMH reportable events policy.

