9.4.4 Risk-Benefit Assessment

This study consists of surveys, interviews and focus groups, and health coaching intervention, and is no more than minimal risk for study subjects. The information gathered in this study will inform development of interventions to improve STI and HIV prevention care delivery to participants. The potential benefit of enhanced care to a disproportionately burdened population outweighs the unlikely, yet potential, risk of loss of confidentiality or psychological distress. Safeguards will be put in place to protect all patient study information and limit any disclosure in the limited and coded dataset and in the final de-identified dataset.

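### Psychological distress is a named risk, but the safety analysis only summarises adverse-event frequencies; the symptom score and chart diagnoses scheduled in both arms have no outcome analysis by arm

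*Combined protocol and SAP*

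**What the plan says.** **Risk.** Section 9.4.1 states that "risks (loss of confidentiality, psychologic distress etc.) to the participants will be monitored by the co-investigators". Section 9.4.4 weighs benefit against the "risk of loss of confidentiality or psychological distress".

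**Safety analysis.** Section 6.3.3 says: "The frequencies of AEs will be summarized, although because this study is minimal risk, few are expected". It gives no split by arm, no denominator and no measure of distress. Its one example of a reportable event is in "any unanticipated or adverse events (i.e. breach of privacy) to the CHOP IRB and NIMH".

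**Ascertainment.** Section 8.1 says that AEs are monitored throughout, without a question, form or schedule. Section 5.3 provides that "if a participant discloses suicidal ideation, homicidal ideation, or abuse during an intervention session, the PI will be notified immediately". It also has staff act when a participant in either arm divulges a risk of harm during the questionnaires, or when harm is suspected. Section 8.2 acts on volunteered information and tracks referrals in REDCap.

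**Contact.** Under section 3.1 and Table 1, both arms have data visits at baseline, 3 and 6 months. Coaching adds sessions at 1 week and 1 month. Section 7.1 lets coached participants reach the coach for a further three months after the last session.

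**Measures in both arms.** Section 5.1.3.1 lists the "Youth Pediatric Symptom Checklist" in the survey battery, which is headed for the baseline, 3-month and 6-month visits. Section 5.1.3.3 lists mental health diagnoses among the chart variables, and Table 1 schedules chart abstraction in both arms at the same three times.

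**Use of the score.** Section 6.3.2 compares self-efficacy between "those with and without mood ratings consistent with depression on the PSC-17", and compares retention between groups that include high depressive symptoms. In both, the score is a predictor.

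**The concern.** The planned AE summary is weak for a named risk in two ways. First, it may be incomplete: with no set question, a distressed participant who says nothing and shows nothing is not counted. Second, if the counts are shown by arm, as readers of a randomized trial will expect, they carry a difference in opportunity to be counted. Coached participants are seen more often, and one of the described disclosure routes (during an intervention session) exists only in their arm.

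The trial nevertheless plans two sources that depend far less on contact with the coach: a symptom score and chart diagnoses, both scheduled alike in the two arms. Neither is reported as an outcome. The direction of any effect on mood is open. Section 7.1 says that many of the skills come from a depression prevention program, so an improvement would go unreported just as a harm would.

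**Working it through.** The plan states no safety figure, so there is none to reproduce. Two illustrations show the size of the problem and what the existing data could deliver.

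**1. Contact effect on AE counts**

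Inputs from the documents: scheduled contact times are 5 for coaching (baseline, 1 week, 1 month, 3 months, 6 months) and 3 for SOC (baseline, 3 months, 6 months). Input assumed: a distressed participant comes to notice with probability *q* at each contact, independently, with distress present throughout. The documents give no value for *q*.

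Proportion detected = 1 − (1 − *q*)^*k* for *k* contacts. With equal true rates, the ratio of expected counts is the ratio of these proportions.

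| *q* | Coaching, *k* = 5 | SOC, *k* = 3 | Ratio |
|---|---|---|---|
| 0.1 | 0.410 | 0.271 | 1.51 |
| 0.2 | 0.672 | 0.488 | 1.38 |
| 0.3 | 0.832 | 0.657 | 1.27 |

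With a true rate of 10% in each arm (7.5 of 75) and *q* = 0.2, the expected counts are 7.5 × 0.672 = 5.0 and 7.5 × 0.488 = 3.7. Counting only contacts after baseline (4 against 2), the ratio is 1.81 at *q* = 0.1 and 1.64 at *q* = 0.2. At *q* = 0.5 with 5 against 3 it falls to 1.11. Open access to the coach is left out of these figures.

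Even with complete ascertainment, a count says little at this size: 67 per arm has about 37% power for 10% against 20%, and about 19% for 5% against 10%.

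**2. Precision of a by-arm PSC-17 comparison**

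Inputs from section 6.4: 75 per arm and up to 10% loss, so 75 × 0.9 = 67.5, taken as 67. Input assumed: baseline to follow-up correlation *r*. Section 9.1.1 places the baseline survey before randomization, so the baseline score is a valid covariate.

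Half-width of the 95% CI, in SD units = t(0.975; 132) × √[(2/67)(1 − *r*²)].

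| *r* | Half-width (SD) |
|---|---|
| 0.3 | 0.33 |
| 0.5 | 0.30 |
| 0.7 | 0.24 |

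With 20% loss (60 per arm, normal approximation) the half-widths are 0.34, 0.31 and 0.26 SD. The planned data would therefore estimate a mean shift in symptoms to about ±0.3 SD.

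**The case against.** The strongest reply is that this is a small, minimal-risk trial, that section 6.3.3 plans only to summarise frequencies, and that no between-arm AE comparison or safety claim is made. That is so. The contact ratio describes what a by-arm display could show; it is not an error in a planned test, and it rests on an assumed *q*.

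Several stronger readings are tempting, and the documents do not support them:

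- *Distress will be missed, or coaching will look worse.* The documents support only that either could happen. Section 5.3 gives SOC participants a route during surveys and lets staff act on reactions or suspected harm, so disclosure is not the only path. Section 9.4.1 adds at least monthly event review during Aim 3.
- *The PSC-17 is the only measure taken alike in both arms.* Chart-abstracted diagnoses and the CRAFFT are too.
- *The AE definition excludes distress because the example given is a privacy breach.* Section 8.2 covers serious events, abuse and thoughts of harm, and section 9.4.2 reports any adverse events to the IRB and NIMH. The example is loose wording.
- *A safety conclusion from this trial is meant to support the next one.* Section 10 speaks of the RCT findings generally.
- *The follow-up scores go unused.* Section 6.3.2 does not say which visit's score forms the groups. What is missing is an analysis of the score as an outcome.

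Three limits on the PSC-17 stand. Section 5.3 says that it has no suicidality item. It is a mood rating, so it may not capture a brief reaction to sensitive questions, which both arms receive in any case. And section 5.1.3.1 has no schedule by instrument: its list includes a coaching satisfaction survey that cannot apply at baseline or to SOC, so collection at all three visits is read from the heading. The score can therefore supplement AE reporting but not replace it.

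**Conclusion.** The point holds as a gap in the safety analysis that is cheap to close. A named risk has no outcome analysis by arm, although two suitable sources are planned in both arms, and the one planned summary has no stated ascertainment method and could differ by arm through contact alone.

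That distortion cannot be sized from the documents; the ratio of about 1.5 to 1.3 applies only under the assumed 0.1 to 0.3 per contact. The precision of about 0.3 SD rests on an assumed correlation of 0.5, 1:1 allocation, the plan's 10% loss, and the PSC-17 being collected as the section heading implies. The primary analysis is not affected.

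**What to change.** In section 6.3.3:

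1. Report the PSC-17 by arm at 3 and 6 months as a baseline-adjusted difference with 95% CI, plus the proportion by arm newly above a cut-off fixed before analysis (section 6.3.2 gives none). Label this descriptive safety, and say that it supplements AE reporting because the score has no suicidality item. State in section 5.1.3.1 that the PSC-17 is given at all three visits in both arms.
2. Tabulate new chart-abstracted mental health diagnoses by arm.
3. Tabulate all post-randomization AEs by arm and by the contact at which they were found (shared visit or coaching-only contact), with a note that contact differs by arm. Do not restrict the comparison to shared visits: that would remove coached participants' disclosures at 1 week and 1 month and could tilt the result the other way.

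The cost is analysis-plan wording, a short analysis of data already planned, and a record of the contact at which each AE was found. No visit or instrument is added. The small downside is a few more descriptive comparisons without multiplicity adjustment.

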6.4 Sample Size and Power

Aim 1: The individual focus group size of 5-8 is informed by consensus methods literature. The goal of the pooled focus group size of ~50 is thematic saturation. The goal of the in-depth interviews is thematic saturation, which could be reached at ~15 participants. If we do not reach saturation at this sample size, or if key themes emerge among subgroups of participants which we wish to further explore, we will continue focus groups and in-depth interviews until saturation is met.

Aim 2: Previous studies demonstrate that 3-6 charts per clinician are sufficient for reliable and valid assessment in CSRs. We propose to interview 25 clinicians and nurses with the goal of achieving saturation of themes, for which this sample size should be sufficient, and will continue if saturation is not met.

Aim 3: We propose a sample size of 150 participants (75 intervention, 75 control – with the possibility of a greater number of intervention than control if we shift to 2:1 randomization) based on the aim of detecting a moderate effect size score difference in the change in modified GSES scores between intervention and control. Given this sample size, and assuming a range of intra-subject correlations across subjects ranging from (0.01 to 0.3), we will have 80% power and a two-sided alpha of 0.05 to detect a 0.7-0.9 standard deviation difference change in GSES scores from baseline and six months by treatment group. And be protected from and up to 10% lost-to-follow-up rate.

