3.2 Allocation to Treatment Groups and Blinding

Aim 1: N/A

Aim 2: N/A

Aim 3: Non-stratified 1:1 randomization will occur at baseline using the REDCap randomization tool based on randomization tables. The study team will not be able to change study groups for participants once randomization has taken place. The randomization will not be blinded to the participants or the study team because of the nature of the intervention.

As mentioned in Section 3, if difficulty retaining coaching participants during the RCT generates a disparity in evaluable participants per arm, the RCT's randomization scheme will be changed to 2:1, intervention vs SOC, to balance numbers of evaluable participants per arm.

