5.2 Efficacy Evaluations

These are the measures that will be used to assess the efficacy of the study intervention

Aim 1: N/A

Aim 2: N/A

Aim 3: The primary efficacy outcome is the difference in change in self-efficacy between baseline and six-month visits for the intervention group versus control, as measured by the modified Generalized Self-Efficacy Scale.

5.2.1 Diagnostic Tests, Scales, Measures, etc.

See the list of CASIs in section 5.1.3.1 above.

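### The 0.7-0.9 SD detectable difference in section 6.4 does not follow from its own inputs: the 0.9 end is not reproduced, and the SD unit is not named

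*Combined protocol and SAP*

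**What the plan says.** Section 6.4 starts from the number to be enrolled: "We propose a sample size of 150 participants (75 intervention, 75 control", with a possible shift to 2:1. It says this number is "based on the aim of detecting a moderate effect size score difference in the change in modified GSES scores between intervention and control", but attaches no value to moderate. The power statement is made "assuming a range of intra-subject correlations across subjects ranging from (0.01 to 0.3"), and it reads: "we will have 80% power and a two-sided alpha of 0.05 to detect a 0.7-0.9 standard deviation difference change in GSES scores". The paragraph ends by allowing for up to 10% loss to follow-up. It gives no formula, no GSES standard deviation, and no indication of whether the SD is that of a single score, of the change, or of a model residual.

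Section 5.2 fixes the contrast: "The primary efficacy outcome is the difference in change in self-efficacy between baseline and six-month visits for the intervention group versus control". Section 6.3.2 describes the outcome as the "outcome variable of continuous score on the modified Generalized Self-Efficacy Scale at baseline", three months and six months, analysed "using mixed effects logistic regression models with a random intercept for patient and a random slope for time". No slope variance is given in either 6.3.2 or 6.4.

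**The concern.** The power sentence in 6.4 is the plan's only statement of what the primary comparison can detect, and a reader with the same inputs should be able to recover it. Two features suggest otherwise. First, 0.9 SD is a large difference for 75 per arm at 80% power. Second, the result is given in SD units without saying which SD, and for a change outcome the choice matters: a single-score SD and a change-score SD differ by a factor that itself depends on the correlation.

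At stake is whether the plan can show that 150 participants serve its stated aim. As written, a reader can neither verify the range nor compare it with the moderate effect that the sample size is meant to detect. The direct effect on recruitment is nil. The loss is in the justification, and in the use of this figure when the later, fully powered trial foreseen in section 10 is designed.

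**Working it through.** **Inputs.** From 6.4: 75 per arm; up to 10% loss, so 75 × 0.9 = 67.5 evaluable per arm; two-sided alpha 0.05; power 80%; intra-subject correlation ρ from 0.01 to 0.3. From 5.2 and 6.3.2: the contrast is the between-arm difference in change from baseline to six months in a continuous score. My assumptions: equal variance at each visit and in each arm, a linear comparison, and a normal approximation.

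**Formula.** Detectable difference = (1.960 + 0.842) × SD × √(1/n₁ + 1/n₂). In change-score units SD = 1. In single-score units SD = √(2(1−ρ)), because the variance of a difference of two equally variable scores is 2(1−ρ).

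**Attempt to reproduce 0.7-0.9.** With 67.5 per arm, √(2/67.5) = 0.1721.

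- Change-score SD: 2.802 × 0.1721 = 0.482, whatever the correlation.
- Single-score SD, ρ = 0.01: 2.802 × 0.1721 × √1.98 = 0.679.
- Single-score SD, ρ = 0.3: 2.802 × 0.1721 × √1.40 = 0.571.

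Using the three-month visit does not change this. In a three-visit linear mixed model with linear time and a random intercept only, the variance of the six-month change is again 1.98 and 1.40, which gives 0.679 and 0.571. Without any loss (75 per arm) the single-score figures are smaller: 0.644 and 0.541.

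**Power at the stated ends** (67.5 per arm, single-score SD):

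| Difference | ρ = 0.01 | ρ = 0.3 |
|---|---|---|
| 0.7 SD | 82.4% | 93.0% |
| 0.9 SD | 96.0% | 99.3% |

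So 0.7 is nearly reproduced at ρ = 0.01, and 0.9 is not reproduced at either correlation. In change-score units, power at 0.9 SD exceeds 99.9%.

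**How far 0.9 is from the inputs.** Evaluable number per arm needed for 0.9 single-score SD at 80% power: 2 × 1.98 × 2.802² / 0.81 = 38.4, so 39 (ρ = 0.01); 2 × 1.40 × 2.802² / 0.81 = 27.1, so 28 (ρ = 0.3). The plan has 67.5.

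Equivalently, for 0.9 to be the 80%-power difference at 67.5 per arm, the change variance would have to be (0.9 / 0.482)² = 3.48 single-score variances. Against 1.98 and 1.40 that is 1.76 and 2.49 times larger.

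**Other routes tried.** t in place of z, ANCOVA, residual-SD units, a one-sided test, and 2:1 allocation (100/50 randomised, 90/45 after 10% loss) were tried at 80% power. The largest value was about 0.72.

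One non-standard route comes close: inflating the variance to 2(1+2ρ), as if the three visits were a cluster, gives 0.689 (ρ = 0.01) and 0.863 (ρ = 0.3). This may be how the range arose, but that is a guess. It is also not valid for this contrast, since correlation within a person reduces the variance of that person's change.

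**2:1 option, for illustration.** If all 150 were randomised 2:1 and each arm lost 10% (90/45), the detectable difference is 0.720 (ρ = 0.01) to 0.605 (ρ = 0.3) single-score SD. With an assumed 40% coaching loss and 10% control loss (60/45), it is 0.777 to 0.654.

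**The case against.** The strongest reply is that the planned model was not reproduced. Section 6.3.2 specifies a random slope as well as a random intercept, and slope variance adds to the variance of change. This stands in part: without a slope variance, the planned model's power cannot be computed from the documents, and 0.57-0.68 cannot simply be put forward as its figure. It does not rescue 0.9, though. An addition large enough to raise the change variance by a factor of 1.76 to 2.49 is a major assumption, and 6.4 mentions none.

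A second reply is that the sentence is harmless, because a design with 96-99% power at 0.9 SD does have at least 80%. That also stands as far as recruitment goes. But 6.4 offers the range as what the design can detect at 80% power, and in that role the upper end is wrong on the stated inputs.

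Three stronger readings are tempting, and the documents do not support them.

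- *The range runs the wrong way with correlation.* Section 6.4 does not pair 0.3 with 0.9. If that pairing was meant, the direction is wrong, because a higher within-subject correlation lowers the variance of change. If the reverse was meant, the direction is right and only the size is off.
- *The trial is underpowered for a moderate effect.* The plan never gives moderate a value. Any benchmark would be the reader's own, and the answer would turn on the unstated SD unit.
- *The 2:1 option leaves the trial short of its claim.* The splits and losses above are assumptions. At correlation 0.01 their results, 0.72 and 0.78, lie inside the stated 0.7-0.9; at correlation 0.3 they are below it.

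**Conclusion.** The point holds as an error in a stated figure together with missing definitions. On the inputs in 6.4, a comparison of baseline to six-month change with 10% loss detects 0.57-0.68 single-score SD, or 0.48 SD of change, at 80% power; the plan states 0.7-0.9 SD. The lower end is close at the lowest correlation. The upper end is reached by no standard calculation from those inputs.

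This rests on equal variances, a linear analysis of the continuous score, and no random-slope variance. If the sponsor assumed a slope variance, the stated range might be recoverable, but only once that variance is disclosed. Under 1:1 allocation and these assumptions the discrepancy is conservative: the design can detect smaller differences than the plan claims. It gives no ground for saying that too few participants are planned.

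**What to change.** First settle the model in 6.3.2, where a logistic model is named for a continuous score; the power figure should follow a linear mixed model for that score. Then recalculate and rewrite the Aim 3 paragraph of 6.4 so that it:

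- names the SD unit, the formula and the variance assumptions, including any random-slope variance;
- says which detectable difference belongs to which correlation;
- gives the moderate target as a number in the same unit.

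If no slope variance is assumed, the 1:1 figure with 10% loss is 0.68 (correlation 0.01) to 0.57 (correlation 0.3) single-score SD, or 0.48 SD of change.

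If the 2:1 option is kept, add a figure for it with the allocation and the loss in each arm stated. Unequal loss is the relevant case, since section 3.2 makes the switch "if difficulty retaining coaching participants during the RCT generates a disparity in evaluable participants per arm".

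The cost is one recalculation and one rewritten paragraph. The sample size stays at 150.
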